Official Title of the study: **Developing New Technologies to Improve ADHD Medication Continuity**

NCT number: **NCT02390791**

Document name: **Analysis Plan**

Date of the document: **11/1/17**

ADHD Enhanced Portal Statistical Analysis Plan

Prepared by: [name]

Date: 11/1/17

Analysis plan approved by:

[name], MEd, MSc
Associate Professor
Division of General and Community Pediatrics
PI ADHD Enhanced Portal Study

11/1/17
Date

The results of the ADHD Enhanced Portal Pilot study Aim 3 will be assessed as described in this document. This statistical analysis plan begins with an overview of the key components of the study including its design, objectives, and outcome measures. This is followed by a detailed description of the statistical analyses that will be utilized to address Aim 3 study hypotheses.

1. Overview of study: This study is a multi-practice, cluster randomized trial to evaluate the effectiveness of an Enhanced ADHD portal. Practices that agree to participate in the study were randomized 1:1 to receive either the intervention (enhanced ADHD portal) or the control group (standard portal) prior to subject enrollment. We used a covariate-constrained randomization procedure to ensure that the intervention and control practices were balanced with respect to: 1) number of health care providers and 2) average percentage of Medicaid patients (Ivers et al. 2012). We planned to enroll a total of 80 children newly diagnosed with ADHD from 8 practices in this trial (40 from the intervention practices and 40 from the control practices).

1.1 Study Objective: Evaluate the general effectiveness of the intervention (e.g. enhanced ADHD portal), compared to control (e.g. standard portal), on medication continuity as measured by prescription records and other more proximal outcomes during the first six months of treatment.

Working hypothesis 1: compared to the control group, the intervention group will have greater medication continuity as measured by number of days covered with medicine.

Working hypothesis 2: compared to the control group, the intervention group will have greater proportion with parent entered data to track response to treatment.

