2.3.2 Primary outcome analysis

Primary outcome: Medication continuity as measured by number of days covered with medicine within 6 months of medication start.

- Number of days covered with medicine is calculated from audit of prescriptions written during the first 6 months of medication treatment.

For the primary outcome, the dependent variable will be a count of the number of days covered with medicine within 6 months of ADHD medication start date. Differences between intervention and control groups on this outcome will be evaluated using a generalized linear model assuming a Poisson distribution with a log link function. The number of days from start of medication to end of study will be included in the model as an offset. Other potential covariates (e.g. baseline characteristics of child age, and race with large differences between groups) will be included in a secondary analysis model evaluating the effectiveness of the intervention.

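### Outcome models ignore the practice-level design: no practice term, and a covariate rule that tends to screen out the two factors used to constrain the randomization

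*SAP*

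**What the plan says.** Section 1 of the SAP states the design: "This study is a multi-practice, cluster randomized trial to evaluate the effectiveness of an Enhanced ADHD portal". On size: "We planned to enroll a total of 80 children newly diagnosed with ADHD from 8 practices in this trial", 40 children per arm. On allocation: "We used a covariate-constrained randomization procedure to ensure that the intervention and control practices were balanced", and specifically "balanced with respect to: 1) number of health care providers and 2) average percentage of Medicaid patients". Both factors are properties of the practice.

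Section 2.3.2 says that arm differences on days covered "will be evaluated using a generalized linear model assuming a Poisson distribution with a log link function". The only other specified element is the offset: "The number of days from start of medication to end of study will be included in the model as an offset". Section 2.3.3 uses logistic regression for the binary secondary outcome and Poisson regression for the two counts. None of these models has a practice effect, a cluster-robust variance or a practice-level summary.

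Covariates are governed by observed imbalance. Section 2.3.1 admits baseline characteristics on which the arms differ greatly. Sections 2.3.2 and 2.3.3 place them in a secondary model, with age and race as examples. Neither constraining factor is named in any model, nor in the list of practice characteristics to be summarized in 2.3.1.

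**The concern.** There are two mismatches between design and analysis, and they act in opposite directions.

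1. Practices were randomized, but children are analysed as if independent. Children in one practice share clinicians and prescribing habits, so the arm comparison is less precise than 80 independent observations would make it. Standard errors are too small and false positives too frequent.

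2. The two factors thought important enough to constrain the allocation are left to a rule that looks for imbalance. Constraining makes large imbalance unlikely, so the rule will tend to pass them over. Once practice is the unit, leaving out a factor that predicts outcome keeps its variation in the error term although the design has largely removed it from the comparison. Standard errors are then too large, and the balance bought at randomization is not turned into precision.

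The first defect is the larger and affects the plan as it stands. The second appears only after the first is repaired.

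**Working it through.** **Inputs from the SAP.** 8 practices, 80 children, 1:1 allocation, so 80 / 8 = 10 children per practice and 4 practices per arm. The SAP gives no ICC, SD, effect size, alpha or power, so there is no figure of its own to reproduce.

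**Assumptions.** Mean about 110 days covered, SD 50, values limited to 0-183, full follow-up, two-sided 5%. Allocation is drawn from the 18 best-balanced of the C(8,4) = 70 possible splits. R2 is the share of between-practice variance explained by the two factors.

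**Step 1, clustering.** Design effect = 1 + (10 - 1) x ICC:

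- ICC 0.05: 1 + 9 x 0.05 = 1.45; effective N = 80 / 1.45 = 55
- ICC 0.10: 1.90; effective N = 42
- ICC 0.20: 2.80; effective N = 29

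**Step 2, type I error (%) with no true effect, 2000 trials per row.** Simulation error near 5% is about sqrt(0.05 x 0.95 / 2000) = 0.5 percentage points.

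| ICC | R2 | Planned Poisson | Poisson + 2 factors | Poisson, dispersion scaled | Scaled + 2 factors | Practice t-test, 6 df | Practice, adjusted, 4 df |
|---|---|---|---|---|---|---|---|
| 0 | 0 | 62.3 | 64.0 | 4.7 | 4.6 | 5.2 | 5.4 |
| 0.05 | 0 | 72.6 | 72.2 | 11.2 | 11.8 | 5.2 | 5.8 |
| 0.05 | 0.5 | 69.4 | 70.2 | 8.2 | 8.1 | 3.0 | 4.8 |
| 0.05 | 0.9 | 66.4 | 65.4 | 6.9 | 6.2 | 3.4 | 5.6 |
| 0.10 | 0 | 75.5 | 75.6 | 15.8 | 16.2 | 5.1 | 5.0 |
| 0.10 | 0.5 | 73.8 | 72.6 | 11.0 | 10.5 | 3.3 | 4.6 |
| 0.10 | 0.9 | 68.6 | 66.0 | 7.6 | 6.3 | 1.7 | 4.2 |

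Three readings follow.

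- The very high rates under the planned Poisson model come mostly from fixing the variance at the mean. They are present at ICC 0 and depend on the assumed SD: 36% at SD 20 and 73% at SD 60, with ICC 0.05 and R2 0.5.
- The effect of ignoring practice is seen in the dispersion-scaled column, which is correct at ICC 0 and rises to 15.8% at ICC 0.10. Over ICC 0.05-0.20 the range is about 7-26%.
- Adding the two factors to a child-level model changes little (69.4 to 70.2; 8.2 to 8.1). With practice as the unit, their omission lowers the rate below 5% only where R2 is above 0. Over ICC 0.10-0.20 and R2 0.5-0.8 the unadjusted rate is about 1-4%.

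**Step 3, cost of adjustment.** A comparison of 8 practice means has 8 - 2 = 6 df; with two practice-level covariates, 8 - 4 = 4 df. The critical t rises from 2.45 to 2.78. Power at practice level for a 0.6 SD effect:

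| ICC | R2 | Without factors | With both |
|---|---|---|---|
| 0.01 | 0.2 | 0.59 | 0.49 |
| 0.01 | 0.8 | 0.58 | 0.52 |
| 0.05 | 0 | 0.46 | 0.38 |
| 0.05 | 0.3 | 0.45 | 0.41 |
| 0.05 | 0.5 | 0.45 | 0.43 |
| 0.05 | 0.8 | 0.45 | 0.47 |
| 0.10 | 0.2 | 0.38 | 0.34 |
| 0.10 | 0.3 | 0.37 | 0.36 |
| 0.10 | 0.5 | 0.35 | 0.39 |

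Adjustment loses power at ICC 0.01 throughout, breaks roughly even at R2 about 0.5 for ICC 0.05 and about 0.3 for ICC 0.10, and gains above that. At ICC 0.20 with R2 0.5-0.8 the gain is large: from about 0.2 to 0.32-0.44.

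**The case against.** The strongest reply is that, with 8 practices in a pilot, spending 2 of 6 degrees of freedom on covariates whose relation to outcome is unknown is a poor bargain, and that leaving them out is a defensible choice. For mandatory adjustment in the primary model, this stands: the second table shows a loss over a wide and plausible range. It does not excuse the missing practice term, and it does not justify letting observed imbalance decide whether design factors enter the adjusted model that the plan already has.

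A permutation test restricted to the acceptable allocations would respect the design without spending degrees of freedom. Its usefulness depends on how many allocations were acceptable, which the SAP does not say. With 18, counting mirror images together, the smallest two-sided p-value is 2 / 18 = 0.11, so 5% could not be reached; at least 40 would be needed (2 / 40 = 0.05).

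The imbalance rule is also not confined to child-level variables, and constraint limits imbalance without abolishing it. So the rule tends to exclude the two factors; it does not exclude them with certainty.

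A reader might infer that child insurance, already summarized at baseline, can stand in for the Medicaid factor and save a degree of freedom. The documents do not support this: the allocation was constrained on the practice's average percentage, a different variable, and the substitute has not been evaluated.

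**Conclusion.** The point holds in two parts. First, the models in 2.3.2 and 2.3.3 do not treat practice as the unit although practices were randomized, so the planned intervals are too narrow. In the simulation of days covered, ignoring practice alone takes type I error to about 7-26% at ICC 0.05-0.20, before any error from the fixed Poisson variance. Second, the plan says nothing of the two constraining factors after the allocation, and its covariate rule tends to screen them out. With practice as the unit, this makes the test conservative, about 1-4% at ICC 0.10-0.20 and R2 0.5-0.8, and has no material effect on the error rate if the factors do not predict outcome.

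A reader might infer that omitting the factors is what makes the planned error bars wrong, or that the planned test is conservative. Neither follows. The planned test errs in the other direction, and adding the factors to it leaves the error rate nearly unchanged.

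ICC, SD, R2 and the share of allocations retained are assumptions. The direction of each effect was the same over the ranges tried, but the sizes depend on them. The simulations cover days covered or a continuous outcome; the binary and count outcomes of 2.3.3 were not simulated, and for them the argument rests on the shared design.

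**What to change.** In 2.3.2 and 2.3.3:

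- Make practice the unit of inference, either by analysing practice-level summaries or by a mixed or GEE model with a small-sample correction suited to 8 practices.
- Pre-specify number of providers and average percent Medicaid in the covariate-adjusted model, whatever the observed imbalance, and report results with and without them.
- State which of the two results is primary, and acknowledge the trade-off: adjusting for both at practice level takes 6 df to 4 and lowers power if the factors explain little.

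The cost is SAP wording. Both factors were needed for the allocation, so no new data are required. The SAP is dated 11/1/17, after the study end date of 9/24/17 in 2.2.3. If the analysis has already been run as written, the change belongs in the report of deviations that 2.1.1 calls for.

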1.2 Outcome measures

Primary

- Medication continuity as measured by number of days covered with medicine within 6 months of medication start.
 - Number of days covered with medicine is calculated from audit of prescriptions written during the first 6 months of treatment.

Secondary

- Proportion with parent entered data to track response to treatment
 - Entered data is defined by completion of at least one parent-completed Vanderbilt (VADPRS) between medication start to 6 months post medication start
- Total number of measures completed by parents to track child response to treatment from date of medication start to 6 months post medication start
 - Measures completed are defined by completion of the Vanderbilt (VADPRS)
- Number of family portal logins from date of registration to 6 months post medication start.

1.3 Intervention Fidelity measures

Intervention group only

- Proportion of parents who completed the Shared Decision-Making component
- Proportion of parents who selected an outcome measure (defined as set a behavior to be tracked)

Enhanced Portal SAP Aim 3

Version 1.1, 11/1/17

pg. 2

- Proportion of parents who entered monitoring data (defined as filled in behavior rating data)
- Proportion of parents who received text messages
- Proportion of parents who used the social forum (starting 3/6/16)

1.4 Schedule of visits and time points of interest

- Registration on the portal (usually before consent)
- Consent date
- Baseline survey (baseline, after consent, usually a few days after)
- Medication start (varies by subject)
- 6 months post medication start, 6-month survey (completion)

1.5 Data Management

CCHMC CRC will guide data management for this project as described in the study protocol.

1.6 Interim Safety Analyses

No interim analyses are planned for this study.

2. Statistical Reports

2.1 Report Generation

2.1.1 Deviations from Statistical Plan

The final statistical reports will describe and justify any deviations from the original statistical plan described herein.

2.1.2 Software

The statistical reports will be prepared using SAS 9.4 and R 3.3 under Microsoft Windows operating system.

2.2 Analysis Populations

2.2.1 Screen Failures

Subjects who are recruited but do not give written consent are considered screen failures. Subjects who give informed written consent but are determined ineligible post-consent are considered screen failures. Screen failures will not be included in the analysis.

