2.2.2 Intent-to-Treat (ITT) Population

The ITT population is defined as all subjects who consented and started ADHD medication.

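### The SAP's exclusion of children ruled ineligible after consent conflicts with its own ITT definition and permits exclusions after allocation

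*SAP*

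**What the plan says.** Section 2.2.1 covers two groups of screen failures. The second is the one at issue: "Subjects who give informed written consent but are determined ineligible post-consent are considered screen failures". The consequence follows at once: "Screen failures will not be included in the analysis".

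Section 2.2.2 sets a different boundary: "The ITT population is defined as all subjects who consented and started ADHD medication". It carries no eligibility condition.

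The opening of Section 2.3 gives a third wording. It keeps subjects in their allocated groups whatever intervention they received, but applies this only to those who are both enrolled and eligible.

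On timing, Section 1 states: "Practices that agree to participate in the study were randomized 1:1", and places this before subject enrolment. Section 1.4 notes that portal registration usually precedes consent, and lists medication start after consent and the baseline survey.

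Section 2.2.6 requires the reason for any exclusion, the person who decided it and its extent to be passed to the statistical team. Section 2.3.1 promises counts of those consented or registered and of those withdrawn, with a summary of the withdrawals.

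**The concern.** A screen failure is ordinarily a pre-allocation event, and removing it does no harm to a randomised comparison. Here the label is also applied to children who have consented in practices whose arm is already fixed. These are post-allocation exclusions.

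Two things are at stake. First, the analysis set is not uniquely defined: two analysts following different sections could report different denominators for the primary outcome. Second, if rulings of ineligibility fall unequally on the two arms, and the children removed differ in days covered from those who stay, the comparison of medication continuity is biased.

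**Working it through.** **Setting the rules side by side.** Take a child who consented and started ADHD medication.

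| Section | Child never ruled ineligible | Child ruled ineligible before starting medication | Child ruled ineligible after starting medication |
|---|---|---|---|
| 2.2.1 | in | out | out |
| 2.2.2 (ITT) | in | not ITT at the time of the ruling | in |
| 2.3 | in | out | out |

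The sections disagree only in the last column. There, two remove the child and one keeps the child, and the SAP does not say which governs.

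**Timing.** Practices were randomised before enrolment, and a post-consent ruling comes after enrolment, so it always comes after allocation. The arm is a property of the practice, so anyone who knows the practice and its assignment knows the arm. The SAP is silent on whether the person who rules on eligibility is masked.

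**Size.** The SAP states no figure on this point to reproduce. It gives no expected mean, SD or number of exclusions. Its only usable input is the planned 40 children per arm (80 in total, Section 1). The rest is assumed: no true effect, the same mean M in both arms, and k children removed from one arm only, each g days below that arm's mean.

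Shift in the arm mean = k × g / (40 − k).

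- M = 120, 3 children with 40 days each (g = 80): (40 × 120 − 3 × 40) / 37 = 4680 / 37 = 126.5, a shift of 6.5 days.
- M = 120, 5 such children: (4800 − 200) / 35 = 4600 / 35 = 131.4, a shift of 11.4 days.

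Range for g from 30 to 90 days:

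| k removed from one arm | Shift in days |
|---|---|
| 1 | 0.8 to 2.3 |
| 2 | 1.6 to 4.7 |
| 4 | 3.3 to 10.0 |
| 6 | 5.3 to 15.9 |

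**Against sampling error, for the 3-child case.**

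- Between-child SD assumed to be 50 days: SE = 50 × √(1/40 + 1/37) = 11.4 days, and 6.5 / 11.4 = 0.57, about 0.6 SE.
- Poisson variance, as the primary model in Section 2.3.2 assumes: SE = √(120/40 + 120/37) = 2.5 days, and 6.5 / 2.5 = 2.6 SE.

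Both lines ignore clustering by practice and the offset. The shift is the same in each; only the yardstick changes.

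**The case against.** The strongest reply is that the sections can be read in sequence: Section 2.2.1 first removes screen failures, Section 2.2.2 then defines ITT among the rest, and Section 2.3 states the combined rule. On that reading ITT means eligible, consented children who started medication. This is a fair reading, and Section 2.3 does side with Section 2.2.1. But Section 2.2.2 says all subjects and nothing subordinates it, and the reading settles only the wording. The exclusion would still come after allocation.

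It can also be said that eligibility criteria, and who confirms them and when, belong in the protocol, which is not at hand. That stands, and no fault is found with their absence. The point rests on what the SAP itself states.

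A reader might go further in several ways that the document does not support:

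- **That a diagnosis revised, or medication stopped, months into treatment makes a child ineligible.** No section says so. The ordinary sense of the screen-failure rule is an entry criterion found not to have been met, and later protocol violations and withdrawals have their own section, 2.2.6.
- **That the portal was already in use.** Section 1.4 speaks of registration, and the control arm has a portal too.
- **That whoever ruled knew the arm and the prescription course.** Knowledge of the arm is a likely inference from practice-level allocation. Knowledge of prescriptions is possible but not stated.
- **That bias occurred.** Nothing shows how many such exclusions there were, or that they were selective. Similar removals in both arms would give little or no net shift.

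Section 2.2.6 does make exclusions traceable. It does not prevent selective ones, and neither it nor Section 2.3.1 asks for post-consent screen failures by arm.

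**Conclusion.** The point holds in a limited form. For a child who started medication and was then ruled ineligible, Section 2.2.2 conflicts with Sections 2.2.1 and 2.3. Following the latter two excludes children after allocation, probably with the arm inferable. This can bias the primary comparison if rulings differ by arm; the SAP gives no evidence that they did.

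The size is illustrative. Under one-arm removal of 3 to 5 children, each 80 days below a mean of 120, the arm mean moves by 6.5 to 11.4 days. The 6.5-day shift is about 0.6 SE with an assumed SD of 50 days. The larger ratio of 2.6 under Poisson variance depends on the model's having no extra between-child variation and should not be read as a predicted false-positive result. The matter should be corrected because the change is specific and cheap, not because harm has been shown.

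**What to change.** 1. In Section 2.2.1, limit post-consent screen failures to children who failed an entry criterion on facts dated on or before consent. The ruling should be made without reference to prescription data and, where feasible, without the arm. Full masking may be impractical, since the practice reveals the arm.
2. Align Sections 2.2.2 and 2.3 so that every other consented child who started medication is analysed as allocated. Both need amending: changing only Section 2.2.2 would leave Section 2.3 in contradiction.
3. In Section 2.3.1, report post-consent screen failures by arm with the reason. Section 2.2.6 already collects reasons for exclusions.
4. Repeat the primary model with the excluded children who started medication restored, where consent and chart data allow.

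The cost is some wording, one table and one sensitivity run. A few extra chart audits may be needed, because the audits promised in Section 2.2.5 are for study participants and may not have covered screen failures. Keeping a few children later judged ineligible may dilute the effect slightly.

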2.2.2 Intent-to-Treat (ITT) Population

The ITT population is defined as all subjects who consented and started ADHD medication.

2.2.3 Completion

Patient will be considered to have completed the study once the patient completes the 6-month post medication survey or study end date on 9/24/17.

2.2.4 Outliers

The data management and statistical analysis teams will identify subjects having data values that appear to be potential outliers. These values will be sent to the research coordinators for verification. Clear

Enhanced Portal SAP Aim 3

Version 1.1, 11/1/17

pg. 3

identification of a value as an outlier will be based on medical judgment as well as on statistical grounds. In the event that outlier values are identified, any analysis using the actual values will be followed by an analysis that reduces the outlier effect.

2.2.5 Missing data

We will complete chart audits of prescriptions written to calculate our primary outcome for all study participants unless consent is withdrawn. Our approach for handling missing data will be to first assess consent withdrawal rates and evaluate whether or not the rates are very different between the two arms of the trial. If the rates/reasons are similar, we will perform the analysis assuming *Missing Completely at Random (MCAR)*, i.e., the propensity for a data point to be missing is completely random such that there is no relationship between whether a data point is missing and any values in the data set, missing or observed (missing data are a random subset of the data). If consent withdrawal rates are very different between the two arms of a trial, then our results will be limited by concerns about potential bias.

For secondary outcomes, missing outcome data could occur for several reasons such as item nonresponse, lost to follow-up, and data collection errors. Secondary outcomes are supportive and exploratory in nature, thus we will not impute missing secondary outcomes. Results of secondary outcomes will be limited by potential bias due to missing data.

